7.1.5.4.3 Run-in (Visit 2/Week-2)

Subjects' prior/concomitant medications and adverse events will be reviewed. Vital signs, body weight, and height will be measured and laboratory samples will be obtained.

Note: If Visit 2/Week -2 occurs ≤2 weeks after Visit 1/Screening, it is not necessary to repeat A1C, hematology and chemistry panel tests at Visit 2/Week -2. The Visit 1 results from these assessments may be used to satisfy entry criteria (see Section 6, Trial Flow Chart).

A full physical exam, locally read 12-lead ECG and postural blood pressure and pulse will be performed.

All non-washout subjects (these subjects will not have a Visit 1A) will (1) have diet/exercise counseling, (2) receive glucose meters and training in performing SMBG, and (3) receive instruction on hypoglycemia symptoms, hypoglycemia management, and completion of the HAL.

All non-washout subjects will be instructed to monitor their fingerstick glucose concentrations with a frequency determined appropriate by the investigator (based upon his/her assessment of the subject's glycemic control) with a minimum of two fasting determinations per week.

Subjects undergoing AHA washout (who previously received dietary counseling/glucose meters/SMBG training/HAL training at Visit 1A) will have SMBG measurements, and HAL reviewed at Visit 2/Week -2. Appropriate die/exercise counseling will also be performed.

See sections 5.7.1 and 7.1.1.8.2 and 7.1.1.8.3 for additional information regarding dietary/and exercise counseling, HAL training and SMBG training, respectively.

Subjects who meet all enrollment criteria applicable through Visit 2/Week-2 (as detailed in Section 5.1) will enter the 2-week, single-blind, placebo run-in period. The placebo run-in may be initiated at Visit 2/Week -2 while laboratory data, including A1C, are pending, but randomization may not occur until all eligibility criteria are confirmed.

The first doses of single-blind placebo must be taken as witnessed doses in the clinic visit after completion of all **Visit 2/Week -2** procedures and fasting blood samples. Subjects will then be dispensed single-blind investigational product (MK-8521 180 µg and MK-8521 300 µg matching placebos) and instructed to take one injection (0.1 mL) per day from each vial at approximately the same time of day in the morning for two weeks prior to randomization. Subjects should be reminded to withhold single-blind investigational product on the day of **Visit 3/ Day 1**.

7.1.5.5 Treatment Period (Visit 3 through Visit 10)

7.1.5.5.1 Randomization (Visit 3/Day 1)

At **Visit 3/Day 1**, subjects who meet all trial enrollment criteria (see Section 5.1) will have all baseline laboratory tests and trial procedures performed and will be randomized in a 1:1:1:1 ratio to MK-8521 300 μg QD, MK-8521 180 μg QD, placebo QD, or open-label liraglutide QD.

Protocol/Amendment No.: 004-02

Each subject will be assigned only one randomization number; assignment of a randomization number will occur only at **Visit 3/Day 1**.

Investigational product (double-blind and open-label) will be dispensed at Visit 3/Randomization (Day 1). The first dose(s) of investigational product should be taken as a witnessed dose *after* completion of all trial procedures.

7.1.5.5.2 Week 1 through Week 12: Treatment Period

Prior to each trial visit, subjects should be contacted and instructed to withhold investigational product and background metformin on the day of the trial visit (see Section 7.1.5.3). Subjects should continue to take their non-trial medications, as directed by their physician.

The investigational product doses must be taken sub cutaneous in the morning at approximately the same time each day. If a subject misses a dose of investigational product during the trial, they should be instructed to take it as soon as they remember unless it is time for the next dose. Subjects should be instructed not to "make up" for the missed dose by taking two doses at the same time.

Note: See **Section 5.2.2** for timing of dosing investigational product on the day of trial visits.

7.1.5.6 Follow-up Day 14: Post Treatment Visit

A clinic visit will be performed 14 days after the last dose of investigational product to collect specific laboratory measurements (see Trial Flow Chart, Section 6.0), SAEs, body weight, and vital signs (BP and HR).

7.1.5.7 Follow-up for Subjects Who Discontinue Investigational Product

Subjects who prematurely discontinue investigational product (blinded or unblinded) should be followed according to Section 5.9.1.

7.2 Assessing and Recording Adverse Events

An adverse event is defined as any untoward medical occurrence in a patient or clinical investigation subject administered a pharmaceutical product and which does not necessarily have to have a causal relationship with this treatment. An adverse event can therefore be any unfavourable and unintended sign (including an abnormal laboratory finding, for example), symptom, or disease temporally associated with the use of a medicinal product or protocol-specified procedure, whether or not considered related to the medicinal product or protocol-specified procedure. Any worsening (i.e., any clinically significant adverse change in frequency and/or intensity) of a preexisting condition that is temporally associated with the use of the Sponsor's product, is also an adverse event.

Changes resulting from normal growth and development that do not vary significantly in frequency or severity from expected levels are not to be considered adverse events. Examples of this may include, but are not limited to, teething, typical crying in infants and children and onset of menses or menopause occurring at a physiologically appropriate time.

Protocol/Amendment No.: 004-02

Sponsor's product includes any pharmaceutical product, biological product, device, diagnostic agent or protocol-specified procedure, whether investigational (including placebo or active comparator medication) or marketed, manufactured by, licensed by, provided by or distributed by the Sponsor for human use.

Adverse events may occur during clinical trials, or as prescribed in clinical practice, from overdose (whether accidental or intentional), from abuse and from withdrawal.

All adverse events that occur after the consent form is signed but before treatment allocation/randomization must be reported by the investigator if they cause the subject to be excluded from the trial, or are the result of a protocol-specified intervention, including but not limited to washout or discontinuation of usual therapy, diet, placebo treatment or a procedure. From the time of treatment allocation/randomization through 14 days following cessation of treatment, all adverse events must be reported by the investigator. Such events will be recorded at each examination on the Adverse Event case report forms/worksheets. The reporting timeframe for adverse events meeting any serious criteria is described in section 7.2.3.1. The investigator will make every attempt to follow all subjects with non-serious adverse events for outcome.

Electronic reporting procedures can be found in the Electronic Data Capture (EDC) data entry guidelines. Paper reporting procedures can be found in the Investigator Trial File Binder (or equivalent).

7.2.1 Definition of an Overdose for This Protocol and Reporting of Overdose to the Sponsor

In this trial, an overdose is any dose higher than the prescribed dose of MK-8521 or matching placebo and any dose higher than 1.8 mg/day of liraglutide.

If an adverse event(s) is associated with ("results from") the overdose of Sponsor's product or vaccine, the adverse event(s) is reported as a serious adverse event, even if no other seriousness criteria are met.

If a dose of Sponsor's product or vaccine meeting the protocol definition of overdose is taken without any associated clinical symptoms or abnormal laboratory results, the overdose is reported as a non-serious Event of Clinical Interest (ECI), using the terminology "accidental or intentional overdose without adverse effect."

All reports of overdose with and without an adverse event must be reported within 24 hours to the Sponsor either by electronic media or paper. Sponsor Contact information can be found in the Investigator Trial File Binder (or equivalent).

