5.2 Trial Treatment(s)

The treatment(s) to be used in this trial are outlined below in Table 5.

Table 5 Trial Treatment

Dose/ Potency	Drug	Dose	Route of Administration	Treatment Period ⁶	Use
Placebo Run-in (all	Matching placebo for	0.1 mL QD	Subcutaneous	0.1 mL ¹ QD for 2 weeks	experimental (trial drug)
treatment groups)	MK-8521 180 μg, 1.0mL Vial A				
	Matching placebo for MK-8521 300 µg, 1.0mL Vial B	0.1 mL QD	Subcutaneous	0.1 mL ¹ QD for 2 weeks	experimental (trial drug)
MK-8521 180 μg Group	MK-8521 180 μg 0.6 mg/mL, 1.0mL Vial C	0.1 mL QD to 0.3 mL QD	Subcutaneous	Days 1-6: 0.1 mL ¹ QD Days 7-13: 0.2 mL ² QD Days 14-84: 0.3 mL ³ QD	experimental (trial drug)
	Matching placebo for MK-8521 300 μg, 1.0mL Vial D	0.1 mL QD to 0.5 mL QD	Subcutaneous	Days 1-6: 0.1 mL ¹ QD Days 7-13: 0.2 mL ² QD Days 14-20: 0.3 mL ³ QD Days 21-84: 0.5 mL ⁴ QD	experimental (trial drug)
MK-8521 300 μg Group	Matching placebo for MK-8521 180 μg, 1.0mL Vial C	0.1 mL QD to 0.3 mL QD	Subcutaneous	Days 1-6: 0.1 mL ¹ QD Days 7-13: 0.2 mL ² QD Days 14-84: 0.3 mL ³ QD	experimental (trial drug)
	MK-8521 300 μg 0.6 mg/mL, 1.0mL Vial D	0.1 mL QD to 0.5 mL QD	Subcutaneous	Days 1-6: 0.1 mL ¹ QD Days 7-13: 0.2 mL ² QD Days 14-20: 0.3 mL ³ QD Days 21-84: 0.5 mL ⁴ QD	experimental (trial drug)

Protocol/Amendment No.: 004-02

Dose/ Potency	Drug	Dose	Route of Administration	Treatment Period ⁶	Use
Placebo	Matching	0.1 mL QD	Subcutaneous	Days 1-6: 0.1 mL ¹ QD	experimental
Group	placebo for	to 0.3 mL		Days 7-13: 0.2 mL ² QD	(trial drug)
	MK-8521	QD		Days 14-84: 0.3 mL ³ QD	
	180 μg,				
	1.0mL				
	Vial C				
	Matching	0.1 mL QD	Subcutaneous	Days 1-6: 0.1 mL ¹ QD	experimental
	placebo for	to 0.5 mL		Days 7-13: 0.2 mL ² QD	(trial drug)
	MK-8521	QD		Days 14-20: 0.3 mL ³ QD	
	300 μg,			Days 21-84: 0.5 mL ⁴ QD	
	1.0mL				
	Vial D				
Liraglutide	liraglutide	0.6 mg QD	Subcutaneous	Days 1-6: 0.6 mg QD	active-
Group –	6 mg/mL ⁵	to 1.8 mg		Days 7-13: 1.2 mg QD	comparator
Open-Label		QD		Days 14-84: 1.8 mg QD	

- 1. Equivalent to 10 Units in an insulin syringe.
- Equivalent to 20 Units in an insulin syringe.
- 3. Equivalent to 30 Units in an insulin syringe.
- ^{4.} Equivalent to 50 Units in an insulin syringe.
- 5. Liraglutide will be supplied locally by the trial site.
- ⁶. Treatment periods are approximate. See Section 6.0 for allowable visit windows.

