The investigator may delay one step of the dose escalation by one week; however, the dose from each vial must reach 0.3 mL/day no later than Day 21.

Liraglutide Treatment Group

Subjects randomized to open-label liraglutide will begin the trial (Visit 3/Day 1) on 0.6 mg/day liraglutide.

At Visit 4/Day 7, the dose of liraglutide should be increased to 1.2 mg/day.

At Visit 5/Day 14, the dose of liraglutide should be increased to 1.8 mg/day.

The titration regimen for liraglutide may be modified to appropriately manage observed GI intolerance. The liraglutide dose should be titrated to the full target dose (1.8 mg/day) no later than Day 21. Subjects who cannot tolerate the 1.8 mg/day dose of liraglutide may continue in the trial on the 1.2 mg/day dose.

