7.2.3.2 Events of Clinical Interest

Selected non-serious and serious adverse events are also known as Events of Clinical Interest (ECI) and must be reported to the Sponsor.

For the time period beginning when the consent form is signed until treatment allocation/randomization, any ECI, or follow up to an ECI, that occurs to any subject must be reported within 24 hours to the Sponsor if it causes the subject to be excluded from the trial, or is the result of a protocol-specified intervention, including but not limited to washout or discontinuation of usual therapy, diet, placebo treatment or a procedure.

For the time period beginning at treatment allocation/randomization through 14 days following cessation of treatment, any ECI, or follow up to an ECI, whether or not related to the Sponsor's product, must be reported within 24 hours to the Sponsor, either by electronic media or paper. Electronic reporting procedures can be found in the EDC data entry guidelines. Paper reporting procedures can be found in the Investigator Trial File Binder (or equivalent).

Events of clinical interest for this trial include:

- 1. an overdose of Sponsor's product, as defined in Section 7.2.1 Definition of an Overdose for This Protocol and Reporting of Overdose to the Sponsor, that is not associated with clinical symptoms or abnormal laboratory results.
- 2. an elevated AST or ALT lab value that is greater than or equal to 3X the upper limit of normal and an elevated total bilirubin lab value that is greater than or equal to 2X the upper limit of normal and, at the same time, an alkaline phosphatase lab value that is less than 2X the upper limit of normal, as determined by way of protocol-specified laboratory testing or unscheduled laboratory testing.*
 - *Note: These criteria are based upon available regulatory guidance documents. The purpose of the criteria is to specify a threshold of abnormal hepatic tests that may require an additional evaluation for an underlying etiology. The trial site guidance for assessment and follow up of these criteria can be found in the Investigator Trial File Binder (or equivalent).
 - 3. Any subject meeting HR discontinuation criteria (see Section 5.9).

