7.2.4 Evaluating Adverse Events

An investigator who is a qualified physician will evaluate all adverse events with respect to the elements outlined in Table 10. The investigator's assessment of causality is required for each adverse event. Refer to Table 10 for instructions in evaluating adverse events.

Product: MK-8521 81

Protocol/Amendment No.: 004-02

Table 10 Evaluating Adverse Events

Maximum	Mild awareness of sign or symptom, but easily tolerated (for pediatric trials, awareness of symptom, but easily tolerated)					
Intensity						
	Severe incapacitating with inability to work or do usual activity (for pediatric trials, extremely distressed or unable to do usual activities)					
Seriousness	A serious adverse event (AE) is any adverse event occurring at any dose or during any use of Sponsor's product that:					
	†Results in death	r; or				
	†Is life threatening; or places the subject, in the view of the investigator, at immediate risk of death from the event as it occurred [Note: This does not include an adverse event that, had it occurred in a more severe form, might have caused death.]; or †Results in a persistent or significant disability/incapacity (substantial disruption of one's ability to conduct normal life functions); or					
	†Results in or prolongs an existing inpatient hospitalization (hospitalization is defined as an inpatient admission, regardless of length of s hospitalization is a precautionary measure for continued observation. (Note: Hospitalization for an elective procedure to treat a pre-existing condition worsened is not a serious adverse event. A pre-existing condition is a clinical condition that is diagnosed prior to the use of a Merck product and is do patient's medical history.); or					
I	†Is a congenital anomaly/birth defect (in offspring of subject taking the product regardless of time to diagnosis); or					
	Is associated with an overdose (whether accidental or intentional). Any adverse event associated with an overdose is considered a serious adverse event. An overdose that is not associated with an adverse event is considered a non-serious event of clinical interest and must be reported within 24 hours.					

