8.2.5.2 Safety Analyses

The ASaT population and modified ASaT population will be employed for safety analyses. Safety and tolerability will be assessed following a tiered approach by clinical review of all relevant parameters including AEs, predefined limits of change (PDLC), laboratory tests, and vital signs. For all comparisons described below, each of the two doses of MK-8521 will be compared versus placebo and versus liraglutide.

The analysis of safety parameters will follow a tiered approach. The tiers differ with respect to the analyses that will be performed. Safety parameters or adverse events of interest that are identified *a priori* constitute "Tier 1" safety endpoints that will be subject to inferential testing for statistical significance with p-values and 95% CIs provided for between-group comparisons using the Miettinen and Nurminen method [23], an unconditional, asymptotic method. Other safety parameters will be considered Tier 2 or Tier 3. Tier 2 parameters will be assessed via point estimates with 95% CI provided for between-group comparisons; only point estimates by treatment group are provided for Tier 3 safety parameters.

Membership in Tier 2 requires that at least 4 subjects in any treatment group exhibit the event or meet PDLC criterion; all other AEs and PDLCs will belong to Tier 3.

The threshold of at least 4 events was chosen because the 95% CI for the between-group difference in percent incidence will always include zero when treatment groups of equal size

Protocol/Amendment No.: 004-02

each have less than 4 events and thus would add little to the interpretation of potentially meaningful differences. Because many 95% CIs may be provided without adjustment for multiplicity, the CIs should be regarded as a helpful measure to be used as a flagging method—to identify events of potential clinical relevance, that require additional review—and not a formal method for assessing the statistical significance of the between-group differences in AEs and PDLCs.

Table 13 summarizes the analysis strategy for safety endpoints. In addition, as some of the subjects in the MK-8521 300 μ g and liraglutide arms may not get to the full target dose, sensitivity analyses including only subjects with the full dose may be performed for Tier 1 safety parameters.

Table 13 Analysis Strategy for Safety Endpoints

Tier	Safety Endpoint	p-Value	95% CI for Treatment Comparisons	Descriptive Statistics
Tier 1	AE of symptomatic hypoglycemia	X	X	X

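### Overdose is measured against the prescribed dose for MK-8521/placebo but against a fixed 1.8 mg/day for liraglutide, so while liraglutide is prescribed below 1.8 mg, SAE and ECI status can depend on the arm

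*Combined protocol and SAP*

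**What the plan says.** Section 7.2.1 defines overdose for all arms in one sentence: "an overdose is any dose higher than the prescribed dose of MK-8521 or matching placebo and any dose higher than 1.8 mg/day of liraglutide". Where an overdose leads to an adverse event, "the adverse event(s) is reported as a serious adverse event, even if no other seriousness criteria are met". Table 10 in Section 7.2.4 repeats the rule: "Any adverse event associated with an overdose is considered a serious adverse event". An overdose with no clinical symptoms or abnormal laboratory results becomes a non-serious Event of Clinical Interest, to be reported within 24 hours. The ECI list in Section 7.2.3.2 adds no definition of its own. It refers back to "an overdose of Sponsor's product, as defined in Section 7.2.1".

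Dosing is stepped in every arm. For liraglutide, Table 5 begins with "Days 1-6: 0.6 mg QD", and Section 5.2.1.2 continues: "At Visit 4/Day 7, the dose of liraglutide should be increased to 1.2 mg/day". The dose goes to 1.8 mg at Day 14, may be titrated more slowly with Day 21 as the latest date for 1.8 mg, and may stay at 1.2 mg if 1.8 mg is not tolerated. The blinded arms go from 0.1 to 0.2 to 0.3 mL from each vial, then to 0.5 mL from Vial D.

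On analysis, Section 8.2.5.2 says that "each of the two doses of MK-8521 will be compared versus placebo and versus liraglutide". Table 13 gives 95% CIs for AE summary measures in Tier 2.

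**The concern.** The two halves of the definition use different yardsticks. For MK-8521 and placebo the reference moves with the titration step. For liraglutide it is fixed at the top dose, even while the subject is prescribed a third or two thirds of it. A comparable dosing error can then be an overdose in the blinded arms and not in the liraglutide arm.

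The definition also sets seriousness. A mild symptom following such an error is an SAE in a blinded arm and an ordinary AE on liraglutide. With no symptom or laboratory finding, the error is an ECI in one and not reportable as an overdose in the other. Liraglutide is the reference arm for safety and tolerability (Sections 4.1.1 and 4.2.1), and the protocol expects gastrointestinal events at initiation of this drug class (Section 4.2.2.1), which is when the rules differ. What is at stake is a like-for-like reading of SAE and ECI counts between MK-8521 and liraglutide.

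**Working it through.** **Period below 1.8 mg.** Inputs are from Table 5: liraglutide 0.6 mg on Days 1-6, 1.2 mg on Days 7-13, 1.8 mg on Days 14-84. The footnote to Table 8 gives 12 mg for the titration period. Check: 0.6 × 6 + 1.2 × 7 = 3.6 + 8.4 = 12.0 mg over 6 + 7 = 13 days, which agrees.

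**Threshold relative to the prescribed dose.** For liraglutide this is 1.8 divided by the prescribed dose. For MK-8521/placebo it is 1.0 throughout.

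| Days (on schedule) | Liraglutide prescribed | Overdose only above | Largest excess not counted | Blinded arms: overdose above |
|---|---|---|---|---|
| 1-6 | 0.6 mg | 1.8/0.6 = 3.0 × prescribed | 1.2 mg | 1.0 × prescribed |
| 7-13 | 1.2 mg | 1.8/1.2 = 1.5 × prescribed | 0.6 mg | 1.0 × prescribed |
| 14-84 | 1.8 mg | 1.8/1.8 = 1.0 × prescribed | 0 | 1.0 × prescribed |

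**Share of treatment.**
- On schedule: 13/84 = 15.5% of days.
- Titration delayed so that 1.8 mg is reached on Day 21: 20/84 = 23.8%.
- Subject kept on 1.2 mg: the rest of treatment.
- At full dose on Days 14-84 (71/84 = 84.5%) the definitions coincide.

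**Matched errors.**
- Double dose on Days 1-6. Blinded arms: 0.2 instead of 0.1 mL per vial (120 instead of 60 µg on active), an overdose. Liraglutide: 1.2 instead of 0.6 mg, not an overdose.
- Subject held one step down for intolerance who takes the higher step. Blinded arms: 0.5 instead of 0.3 mL from Vial D, an overdose. Liraglutide: 1.8 instead of 1.2 mg, not an overdose.
- Double dose while on 1.2 mg liraglutide: 2.4 mg, an overdose, as in the blinded arms.
- Any excess while on 1.8 mg: an overdose in every arm.

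**How many reclassified subjects would be visible.** The documents give no dosing-error rate, so this is a sensitivity range and not a projection. It supposes that x of 40 subjects in one MK-8521 arm have an SAE only through the overdose rule, and that the liraglutide arm has none. Miettinen-Nurminen 95% CIs for the difference against 0/40 are:

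| x | Difference | 95% CI |
|---|---|---|
| 2 | 5.0% | -4.1% to 16.6% |
| 3 | 7.5% | -1.7% to 20.0% |
| 4 | 10.0% | 0.7% to 23.2% |
| 6 | 15.0% | 5.5% to 29.2% |

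This agrees with the reason in Section 8.2.5.2 for the Tier 2 threshold of 4 subjects: with fewer than 4 in each arm the interval includes zero, and no between-group CI is produced. If 5% of subjects were affected (assumed), the binomial chance of at least 4 of 40 in one arm is 14%. At 2% it is 0.8%.

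**The case against.** The strongest reply is that the definition is explicit, does not contradict itself, and can be defended. MK-8521 had been given for at most 29 days and this is its first outpatient trial in type 2 diabetes, so a stricter trigger for the investigational product is reasonable. That stands as a possible rationale, but the protocol does not state it, and it does not explain why excess placebo volume counts while a tripled liraglutide dose does not.

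The protocol also makes titration errors less likely, with two weeks of practice injections, witnessed doses at the clinic visits where the dose steps up, re-instruction, and telephone and vial-volume checks. This stands, and is a reason to expect small numbers. Section 8.2.5.2 describes the Tier 2 intervals as a flagging device and not as formal tests. Table 13 names only confirmed cardiovascular SAEs, so overall SAE counts enter by inference through the AE summary measures. That stands too.

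A reader might infer more than the text supports:
- That any given dosing error is treated differently throughout the trial. It is not: at 1.8 mg maintenance, and for any liraglutide dose taken above 1.8 mg, the rules agree.
- That a spurious significant SAE difference is to be expected. That needs 4 or more affected subjects in one arm and none on liraglutide, and nothing in the documents supports such a rate. Equal error rates across arms are also doubtful, since liraglutide is one pen injection and the blinded arms draw from two vials.
- That MK-8521 versus placebo is distorted. Both follow the same rule.

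**Conclusion.** The point holds within limits. While the prescribed liraglutide dose is below 1.8 mg, and for doses taken of 1.8 mg or less, an excess dose is an overdose in the blinded arms only. An adverse event resulting from it is an SAE there and not on liraglutide, and an excess dose without symptoms or laboratory findings is an ECI there and not on liraglutide. SAE and ECI counts for MK-8521 versus liraglutide are therefore not produced by one rule, and the tilt is against MK-8521. No other section corrects this.

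The window is 13 of 84 days on schedule, up to 20 of 84 if titration is delayed, and the rest of treatment for subjects kept on 1.2 mg. The size of the effect cannot be computed. Not affected are MK-8521 versus placebo, the recording of the adverse events themselves, and the comparisons of symptomatic hypoglycemia (Tier 1), heart rate and specific AEs such as nausea.

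One related ambiguity remains. The SAE and ECI consequences apply to Sponsor's product. Section 7.2 mentions active comparator medication in defining that term but ties it to manufacture, licensing, provision or distribution by the Sponsor, while Table 5 says that liraglutide is supplied locally by the site. The text does not settle whether the overdose consequences reach liraglutide even above 1.8 mg. If they do not, the asymmetry is wider than described here.

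**What to change.** 1. Reconcile the two parts of Section 7.2.1 so that one reference point defines overdose in all four arms. If the difference is intended, state the reason and say how it will be allowed for when SAE and ECI counts are compared with liraglutide.
2. State in Sections 7.2.1 and 7.2.3.2 whether the overdose rules for Sponsor's product cover locally supplied liraglutide. Without this, a common definition may still not give common reporting.
3. In the SAE summaries, show separately the events that are serious only through the overdose criterion, and keep them in the SAE total. Removing them from the between-arm comparison is unnecessary once the definition is common, and would drop events that the protocol defines as serious.

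This changes a reporting definition and one table. No dose, schedule or treatment rule changes. The cost is a sentence or two in Section 7.2, one more table row and, depending on the reference point chosen, possibly a few more overdose reports.
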